1. GLOSSARY OF ABBREVIATIONS

AEs	Adverse Events
ARC	Academic Research Consortium
CABG	Coronary Artery Bypass Grafting
CCU	Coronary Care Unit
CHF	Congestive Heart Failure
CK	Creatinine Kinase
CRF	Case Report Form
DRS	Disability Ratings Scale
DSMC	Data and Safety Monitoring Committee
EAC	Event Adjudication Committee
ECG	Electrocardiogram
EEG	Electroencephalogram
ESF	Eligibility Screening Form
GCS	Glasgow Coma Score
IV	Intravenous
LV	Left Ventricular
mL	Millilitre
µmmol/L	Micromoles per litre
OHCA	Out-of-Hospital Cardiac Arrest
PCI	Percutaneous Coronary Intervention
ROSC	Return Of Spontaneous Circulation
SAE	Serious Adverse Event
STEMI	ST-Elevation Myocardial Infarction
TH	Therapeutic Hypothermia
UOHI	University of Ottawa Heart Institute

2. SYNOPSIS OF PROTOCOL

Title	Therapeutic Hypothermia following Out-of-Hospital Cardiac Arrest – A randomized trial comparing mild and moderate therapeutic hypothermia
Sponsors	None
Clinical phase	III
Indication	Therapeutic Hypothermia
Objectives	Cooling with moderate hypothermia to a goal temperature of 31°C will result in improved neurologic outcomes compared to mild hypothermia with a goal of 34°C in comatose survivors of OHCA.
Trial design	Single center, randomized, double blinded, parallel group design.
Number of subjects	340
Target population	Out-of-hospital cardiac arrest
Length of study	6 months
Investigational product(s)	None
Comparator “drug”	None
The primary outcome	Death or poor neurologic outcome at 6 months
Event adjudication committee	The following events will be adjudicated by a masked Event Adjudication Committee (EAC): neurologic outcome; death, stroke, and stent thrombosis
Data safety monitoring committee	The DSMC will give advice to the Steering Committee on the safety aspects of the study.

3. SYNOPSIS OF THE TRIAL

3.1 Primary Outcome

The primary outcome of the study will be death or poor neurologic outcome at six months. Neurologic outcome will be assessed using the Disability Ratings Scale (DRS), an 8-item ordinal scale that evaluates functional dependence (See Appendix 8).¹ Neurologic outcome will be assessed by a specialist in rehabilitation medicine at six months. Patients will be judged to have had a poor neurological outcome if the score on the DRS scale is >5 i.e. cannot live independently.

[figure not shown]
3.2 Inclusion Criteria

Any patient >18 years of age who is comatose (Glasgow Coma Score ≤ 8) following out-of-hospital cardiac arrest (OHCA) in whom the treatment plan includes therapeutic hypothermia (TH). The University of Ottawa Heart Institute Therapeutic Hypothermia protocol will guide in patient selection. However, patients will be recruited, irrespective of initial rhythm.

3.3 Exclusion Criteria

1. Patients residing in a Nursing Home or patients unable to reside independently,
2. Intracranial bleed responsible for the cardiac arrest,
3. Severe coagulopathy with clinical evidence of major bleeding,
4. Coma that is not attributable to cardiac arrest,
5. Pregnancy,
6. Life expectancy of < one year due to any cause unrelated to the cardiac arrest,
7. Known coagulation disorder (i.e. INR >2.0, platelets <100,000 / mm³),
8. Participation in a study with another investigational device or drug < four weeks,
9. The Endovascular cooling (ZOLL Thermogard XP) device is not available.

3.4 Study Design

3.5 Summary

This is a single-center, randomized, double-blind investigator initiated prospective clinical trial to be performed at the University of Ottawa Heart Institute (UOHI). The patients for this study will be recruited amongst comatose survivors of OHCA who are admitted at the UOHI. The aim of this study is to determine whether neurologic outcomes at six months are improved with moderate (31°C) versus mild (34°C) TH following ROSC in patients suffering OHCA, with ROSC defined as the resumption of sustained perfusing cardiac activity. The primary outcome will be the proportion of patients experiencing death or a poor neurologic outcome at six months after out of hospital cardiac arrest.

3.6 Statistical Analyses

3.6.1 Sample size

A total of 340 patients will be required to detect an absolute 15% risk reduction (30% relative risk reduction) in the primary outcome based on an anticipated event rate of 50% in the mild hypothermia group and of 35% in the moderate hypothermia group using a chi-square test for comparing proportions with alpha set of 0.05 and a power of 80%.

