4.2.4 Randomization

Randomization will be performed in a 1:1 fashion by sealed opaque envelopes and treatment assigned by random number generation done in blocks. Patients will be randomized immediately following insertion of the endovascular cooling catheter. Because patients with ventricular tachycardia (VT) or ventricular fibrillation (VF) have better survival than other rhythms¹⁰ patients will be stratified based on their initial rhythm. Patients with an initial rhythm of either VT or VF will be randomized from a different series of envelopes than patients with an initial rhythm of asystole or pulseless electrical activity (PEA). The two different series of randomization

envelopes will be identifiable and differentiable by coding (ie. VT/VF randomization codes will begin by the number 1, while randomization codes for asystole/PEA will begin by the number 2). This will ensure balancing in the groups in this important prognostic factor.

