4.7 Pre-specified subgroups

The following pre-specified subgroups will be analyzed at the end of the study:

1. Ventricular tachycardia or ventricular fibrillation as initial rhythm
2. ST segment elevation myocardial infarction as index event
3. Patients taken to the cardiac catheterization laboratory within 12 hrs of the cardiac arrest event
4. Patients undergoing percutaneous coronary intervention
5. Patients age >75yrs

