7. STATISTICAL AND ANALYTICAL METHODS

All analyses on the primary outcome and its components will be performed on an intention-to-treat. The primary outcome will be compared between treatment arms using a significance level of 5% and a power of 80%. Secondary outcomes will be examined using parametric or non-parametric statistics as appropriate for the scale of measurement of the dependent variables. Analyses will be conducted using SAS.

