7.1 Hypothesis Testing

Primary and secondary efficacy parameters will be evaluated for treatment-associated differences between the two groups. The null hypothesis states that there will be no between treatment difference. The

alternate hypothesis states that moderate TH will be significantly more effective than the mild TH at reducing the number of primary outcome events at six months.

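### Randomization is stratified by initial rhythm, but no primary analysis uses the strata; the only test named is an unstratified chi-square

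*Combined protocol and SAP*

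**What the plan says.** Section 4.2.4 describes the allocation: "Randomization will be performed in a 1:1 fashion by sealed opaque envelopes and treatment assigned by random number generation done in blocks". It adds that "patients will be stratified based on their initial rhythm". VT/VF patients draw from one series of envelopes and asystole/PEA patients from another, and the leading digit of the randomization code (1 or 2) identifies the series. The stated purpose is balance: "This will ensure balancing in the groups in this important prognostic factor". The block size is not given.

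Section 7 says of the primary analysis only that it is by intention to treat, is run in SAS, and that "The primary outcome will be compared between treatment arms using a significance level of 5% and a power of 80" per cent. Section 7.1 adds "Primary and secondary efficacy parameters will be evaluated for treatment-associated differences between the two groups". Section 7.2 defines who is analyzed. The remark in Section 7 about parametric or non-parametric methods concerns secondary outcomes.

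The one named test is in Section 3.6.1, where the sample size is derived "using a chi-square test for comparing proportions with alpha set of 0.05 and a power of 80" per cent. Section 8.1 repeats the sample size without naming a test. In the planned analyses, rhythm appears only in the subgroup list of Section 4.7: "Ventricular tachycardia or ventricular fibrillation as initial rhythm".

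**The concern.** Blocking within rhythm forces the arms to have nearly the same rhythm mix. The difference in event rates between arms then varies less from trial to trial than it would under simple randomization. An unstratified chi-square does not take this into account. Its standard error still contains the between-rhythm component, so the test rejects too rarely under the null and a confidence interval built on the same variance is too wide. The protocol does the work of stratifying and then plans nothing that collects the benefit.

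There is a second, smaller issue. Because Section 7 names no primary test, the choice between a stratified and an unstratified comparison stays open until the data are in. In a borderline result that choice could decide significance.

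**Working it through.** **1. The plan's own figure.** Inputs from Section 3.6.1: event rates 0.50 and 0.35, alpha 0.05, power 80%. With pooled variance, two-sided, no continuity correction:

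n per arm = [1.960·√(2·0.425·0.575) + 0.8416·√(0.50·0.50 + 0.35·0.65)]² / 0.15² = (1.3702 + 0.5816)² / 0.0225 = 169.3, so 170 per arm and 340 in total. Power at 170 per arm is 80.2%. The stated 340 is reproduced. (The documents do not state sidedness; a one-sided test would need 268.)

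**2. Effect of ignoring the strata, large-sample formula.** Let s be the VT/VF share and g the difference in control event rate between the rhythm groups. Neither is in the documents. Assumed: s = 50%, 65% and 80%; g = 0 to 50 percentage points; overall control rate 50%.

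- Variance the chi-square uses: 0.50·0.50 = 0.25.
- Variance left after stratified, balanced allocation: 0.25 − s(1−s)g².
- Factor by which the standard error is overstated: k = √[0.25 / (0.25 − s(1−s)g²)].
- Actual type I error at nominal 5%: 2·[1 − Φ(1.96k)].

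Example, s = 0.5 and g = 0.30: s(1−s)g² = 0.25·0.09 = 0.0225. Then k = √(0.25/0.2275) = 1.048, so the standard error is 4.8% too large. The type I error is 2·[1 − Φ(2.055)] = 4.0%.

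**3. Simulation at N = 340.** 200,000 trials per scenario, with a common odds ratio giving 35% overall in the moderate arm. Both tests were run without continuity correction. Two allocation models were used: fixed strata with near-equal arms, and random stratum sizes with permuted blocks of four (the block size is an assumption). Ranges run over the shares and, for the simulated columns, both models.

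| Gap g (points) | SE overstated | Type I error, formula | Type I error, chi-square simulated | CMH power minus chi-square power (points) |
|---|---|---|---|---|
| 0 | 0% | 5.0% | 4.6-4.7% | −0.3 to −0.2 |
| 10 | 0.3-0.5% | 4.9% | 4.5-4.6% | −0.4 to +0.1 |
| 20 | 1.3-2.1% | 4.5-4.7% | 4.1-4.3% | +0.2 to +0.6 |
| 30 | 3.0-4.8% | 4.0-4.3% | 3.7-4.0% | +0.6 to +1.7 |
| 40 | 5.6-9.1% | 3.2-3.9% | 2.9-3.5% | +2.0 to +3.6 |
| 50 | 9.1-15.5% | 2.4-3.2% | 2.1-3.0% | +4.0 to +5.8 |

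CMH type I error is 4.6-5.3% throughout. The simulated chi-square sits below the formula even at gap 0 because the counts are discrete; the formula column isolates the part due to ignoring the strata.

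**4. Second parameterization.** The prognostic effect was also set as an odds ratio (asystole/PEA against VT/VF) of 3, 6 or 10, with a VT/VF share of 50-85% and 400,000 trials per scenario. Chi-square type I error was 3.9-4.2%, 2.8-3.8% and 2.0-3.5% respectively; CMH stayed at about 5.0%. Power, chi-square against CMH, was 81.8-82.2% against 82.0-82.9%, 82.6-83.7% against 83.6-86.9%, and 83.3-85.1% against 85.2-90.3%. The pattern is the same.

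**The case against.** The strongest reply is that nothing planned is put at risk. With complete outcomes the chi-square's own power rises with the gap, from about 81% at no gap to about 84% at 50 points. Where CMH gains most, the chi-square already exceeds its 80% target. That is correct, and the loss should be read as efficiency left unused, not as a shortfall against the plan.

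The size also depends on inputs the documents do not give. Up to a 20-point gap the gain is at most 0.6 points and can be slightly negative; gains of 2 points or more appear at gaps of 40 to 50. That stands too. The omission in the text is certain; how much it costs is not.

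It can also be said that stratification was introduced for balance, which it delivers whatever the test; that the chi-square sits under a heading on statistical analyses (3.6) and so is the natural reading of the intended test; and that Section 10.2 promises a blinded statistician, which limits choosing a test by its result. These points soften the concern about an open choice. They do not replace naming the test in Section 7, and they do not make the unstratified variance match the design. Finally, logistic regression with rhythm as a covariate would also use the strata. That is a fair alternative to CMH and does not weaken the point.

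**Conclusion.** The concern holds as a matter of efficiency and pre-specification. The protocol randomizes by rhythm, calls rhythm an important prognostic factor, and plans no primary analysis that uses it. If the chi-square is the primary test, it is valid but conservative. Across the assumed range its standard error is overstated by 0% to 15.5%. CMH would change power by −0.4 to +5.8 points, with the larger gains only where rhythm is strongly prognostic. The treatment comparison is not biased, false positives are not inflated, and 340 is correct for the named test. These sizes rest on the assumed VT/VF share, the assumed gap, a common odds ratio and complete outcomes. The finding that Section 7 leaves the primary test and effect measure unnamed rests on no assumption.

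**What to change.** In Section 7, state that the primary outcome will be compared by a two-sided 5% Cochran-Mantel-Haenszel test stratified by initial rhythm as randomized (VT/VF against asystole/PEA). Report the Mantel-Haenszel risk difference and relative risk with 95% confidence intervals. Keep the unstratified chi-square as a sensitivity analysis. If the investigators prefer rhythm-adjusted logistic regression, it should be named now instead, with its effect measure.

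The cost is wording only. The stratum is already carried in the randomization code, no data or patients are added, and the worst case is a few tenths of a point of power if rhythm turns out to matter little. This point gives no reason to change N from 340.

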4. PROTOCOL

4.1 Background and Rationale

Despite many advances in cardiac care over the past decades, prognosis following out-of-hospital cardiac arrest (OHCA) remains poor. Patients are often left with severe neurologic dysfunction if they survive the index hospitalization.

Two pivotal trials published in the *New England Journal of Medicine* demonstrated improved neurologic outcomes in comatose survivors of OHCA who undergo therapeutic hypothermia (TH).^{2,3} Bernard and colleagues demonstrated an improvement in neurologic function at hospital discharge, while the Hypothermia After Cardiac Arrest group found both favourable neurologic outcomes and a significant improvement in survival at 6 months post-discharge.

Current American Heart Association/International Liaison Committee on Resuscitation guidelines incorporate TH as the standard of care for comatose survivors of OHCA.⁴ Recently, the University of Ottawa Heart Institute published a paper in *Resuscitation* demonstrating a beneficial outcome in patients referred for primary percutaneous coronary intervention (PCI) and TH in patients with OHCA following ST-segment elevation myocardial infarction.⁵ The use of TH (to a target temperature of 32-34 degrees) did not delay door-to-balloon times and neurologic benefit was seen despite the relatively slow cooling times in our retrospective cohort.

Therapeutic hypothermia functions to reduce cerebral metabolic demands, thereby reducing both the hypoxic insult and suppressing chemical reactions associated with reperfusion injury. These reactions include the production of free radicals, excitatory amino acid release and calcium shifts which can lead to apoptosis.⁶ In the normal brain, hypothermia reduces cerebral metabolic rate for oxygen by 6% for every 1°C reduction in brain temperatures >28°C.⁷

Despite evidence that TH is beneficial following OHCA, there is a lack of evidence to guide the targeted temperature during TH. In the two aforementioned randomized controlled trials, Bernard et al targeted a core temperature of 33 degrees, while the HACA group set a target core temperature of 32-34 degrees. A recent retrospective review showed improved neurologic outcomes with mild hypothermia (32°C-34°C) compared to normothermia (<37.5°C).⁸ Animal evidence suggests that even more aggressive cooling to a target temperature of 30°C may be associated with greater neuroprotection.^{8,9}

A recent pilot study by Lopez-de-Sa published in *Circulation* randomized 36 comatose survivors of OHCA to two distinct goal-cooling temperatures, 34°C or 32°C.^{8,10} The primary outcome was survival free from severe dependence (Barthel Index Score \geq 60) at 6 months. They found no difference in the primary outcome between the two groups. Subgroup analysis found that in patients with an initial shockable rhythm, those randomized to 32°C had improved outcomes compared to those assigned to the 34°C target temperature. To date, this remains the first and only randomized controlled trial comparing two different goal-cooling temperatures in comatose survivors of OHCA. Cooling was achieved using the ZOLL endovascular cooling device (ZOLL Medical Corporation, Chelmsford, MA USA). This endovascular cooling device allows the treating physician to cool the patient rapidly to a target core body temperature with accuracy and efficiency. The device can be programmed to actively rewarm the patient after the cooling period is completed.

Despite advances in cooling mechanisms and comprehensive coronary care, patients surviving OHCA continue to experience poor outcomes from a neurologic perspective. The importance of TH is paramount in this high-risk population, and despite evidence of benefit with TH, the optimal goal temperature continues to remain unknown.

Our center is the single regional cardiac referral center for Eastern Ontario – servicing a population of approximately 1.2 million residents. In 2011, we established a CODE ROSC program to manage patients who suffer OHCA in a coordinated and timely fashion. All patients referred to the UOHI who are comatose following OHCA with no identifiable etiology are candidates for TH in our coronary care unit to preserve neurologic function.

Herein, we propose a randomized controlled trial to determine whether TH with cooling to a lower goal temperature is associated with improved outcomes. We hypothesize that cooling with moderate hypothermia to a goal temperature of 31°C will result in improved neurologic outcomes compared to mild hypothermia with a goal of 34°C in comatose survivors of OHCA.

Therapeutic hypothermia has been shown to improve neurologic outcomes and survival in comatose survivors of OHCA. Nevertheless, outcomes remain poor with as many as 60% of patients either dying or surviving with significant neurologic impairment. Despite many advances in cardiac care, these patients still suffer significant mortality and morbidity as a result of cardiac arrest. Our center has a particular interest in cardiac arrest and the use of TH to provide neuroprotection for these patients. In 2011, we established a "CODE ROSC" program in an attempt to streamline and centralize care for these patients (abstract at 2012 CCC in Toronto).

Current American Heart Association/International Liaison Committee on Resuscitation guidelines incorporate TH as the standard of care for comatose survivors of OHCA. These guidelines recommend a target temperature of 32°C-34°C to provide neuroprotection following cardiac arrest. This degree of therapeutic hypothermia is an effective therapy (compared to placebo), improving neurologic outcomes at six months in comatose survivors of out-of-hospital cardiac arrest. However, the optimal goal temperature for therapeutic hypothermia in these patients has not been investigated in large randomized trial. It is possible that a further reduction in metabolic demand that is associated with cooler temperatures may lead to a clinically significant improvement in patient outcomes.

The proposed study is designed to test the hypothesis that more profound cooling by achieving moderate TH will result in improved neurologic outcomes. Our aim is to answer a clinically important question in a randomized, double-blinded fashion. The trial design respects evidence from previous trials and current international guidelines. We have chosen a design that is inclusive of all patients with cardiac arrest (unless attributable to a proven intracranial bleed) for whom the treating physician wishes to incorporate therapeutic hypothermia as part of the patient's treatment plan. While previous trials have excluded patients who presented with an initial rhythm of asystole or pulseless electrical activity, we have chosen to include these patients in our study as they are routinely treated with TH in most clinical settings. Although there is no data on the use of TH in patients with an initial rhythm of asystole, we believe that these patients should be offered TH and a randomized trial to address the utility of this strategy in these patients. Lastly, our protocol design allows for discontinuation of

Commented [c1]: Reference?

cooling in patients in whom TH may be contributing to worsening clinical condition – however, data from our ROSC database and from the literature suggests this is an infrequent event^{2, 4}.

We believe that this randomized study will provide valuable clinical information for the physician and health care team treating comatose survivors of OHCA.

4.2. Study Design

4.2.1 Study Population

Our proposed study is a single-center, randomized, double-blind investigator initiated prospective clinical trial performed at the University of Ottawa Heart Institute (UOHI). The patients for this study will be recruited amongst comatose survivors of OHCA who are admitted at the UOHI. The aim of this study is to determine whether neurologic outcomes at six months are improved with moderate (31°C) versus mild (34°C) TH following ROSC in patients suffering OHCA, with return of spontaneous circulation (ROSC) defined as the resumption of sustained perfusing cardiac activity.

4.2.2 Inclusion Criteria

Inclusion criteria will be any patient >18 years of age who is comatose (Glasgow Coma Score [GCS] ≤8) following OHCA in whom the treatment plan includes TH. The UOHI and The Ottawa Hospital Therapeutic Hypothermia protocol (See Appendix 9) will guide in patient selection. However patients will be recruited, irrespective of initial rhythm found at the time of the cardiac arrest.

4.2.3 Exclusion Criteria

1. Patients residing in a Nursing Home or patients unable to reside independently,
2. Intracranial bleed responsible for the cardiac arrest,
3. Severe coagulopathy with clinical evidence of major bleeding,
4. Coma that is not attributable to cardiac arrest,
5. Pregnancy,
6. Life expectancy of < one year due to any cause unrelated to the cardiac arrest,
7. Known coagulation disorder (i.e. INR >2.0, platelets <100,000 / mm³),
8. Participation in a study with another investigational device or drug < four weeks,
9. The Endovascular cooling (ZOLL) device is not available.

